### **6.6.2 Missing data**

#### Adverse event data

Missing or partial date information for AEs will be replaced according to general Boehringer Ingelheim (BI) rules described in the BI guidance for handling of missing and incomplete AE dates (2).

#### Partial onset dates from clinical event committee (CEC):

In the unlikely case that only the year is documented, the day and month will be imputed as 01 Jan unless the subsequently derived date is before randomisation; in this case the date of randomisation will be used as start date.

If year and month is present the day will be imputed as first of the month unless the subsequently derived date is before randomisation; in this case the date of randomisation will be used.

#### Death date

For patients with a record of death captured on the electronic case report form (eCRF) with missing or only partial death date from all available sources, the death date will be derived as the latest date of any dates as of: event onset and end dates from either the AE page, or CEC adjudicated onset dates, by using also imputed AE dates, last day known to be alive + 1 day, range of possible days based on partial death date and date of trial completion.

#### Missing information on the date of first administration of trial drug

If the date of first drug administration is missing but the patient was randomised, the date of the first drug administration will be set to the date of randomisation. If the date of first administration is partially missing with the month and year present, the day will be set to the date of randomisation if randomisation was in the same month. If randomisation was in the month prior to the first drug administration the missing day will be imputed as the first day of the month.

#### Missing date of trial completion (=last contact or date of death)

If the date is completely missing the following rules will be applied:

- If a patient has withdrawn informed consent, this date will be imputed by the date of IC withdrawal.
- If a patient died and has not withdrawn consent and is not lost to follow-up, this date will be imputed by the date of death.
- If a patient did not die, the date of trial completion will be imputed by the last date the patient was known to free of non-fatal events. This is defined as the maximum of
  - the last date the patient could be followed up for all non-fatal events as documented in the eCRF
  - last onset or end date of an AE

- Onset of an adjudicated event
- End of treatment
- last visit date (NYHA class, EQ-5D, KCCQ, pregnancy test, vital signs, ECG, or central laboratory reported)

In case of a partially missing date, if the imputed date is before the first day (after the last day) of the month/year given as partial date, the first day (last day) of the month/year will be used.

All other cases need to be assessed by the trial team on an individual patient basis, using the above points as guidance.

#### Missing information on the date of trial medication stop

If the date is partially or completely missing, use the minimum of the following dates:

- End of treatment visit date if available
- Date of death
- Trial completion (last contact date)
- Longest extrapolated treatment duration (assuming 1 tablet/day)
- (in case for partially missing date) Last day of the year/month given as partial date

In case of a partially missing date, if the imputed date is before the first day of the month/year given as partial date, the first day of the month/year will be used.

All other cases need to be assessed by the trial team on an individual patient basis, using the points above as guidance.

#### Missing information on concomitant therapy dates

For incomplete date information generally the midpoint of the possible interval will be used. If only the year is present the day and month will be imputed as 01 July, if year and month is present the day will be imputed as 15. If the year is missing, the date will be considered missing.

If this leads to contradictions for the start or end date of a concomitant therapy (e.g. imputed end date before documented start date) a partial end date will be imputed as the end of the interval or a partial start date will be imputed as the start of the interval in the database to resolve this contradiction.

If the medication is reported as being taken at visit 2 (baseline) and the imputed start/end date contradicts this then the start/end date is imputed to the earliest/latest date respectively if this can resolve the contradiction.

Similarly if the medication is reported as not taken at visit 2 (baseline) and the imputed start/end date contradicts this then the start/end date is imputed to the baseline date/ 1 day prior to baseline respectively if this can resolve the contradiction.

All other cases or conflicting cases resulting from these imputation rules need to be assessed by the trial team on an individual patient basis.

Missing measurement to confirm “sustained” decrease

An eGFR (CDK-EPI)cr reduction is considered sustained, if it is determined by two or more consecutive post-baseline central laboratory measurements separated by at least 30 days (first to last of the consecutive eGFR values). If there is no additional measurement  $\geq 30$  days after the eGFR reduction is observed and the patient dies within 60 days of this measurement, then the eGFR reduction is also considered sustained.

Pharmacokinetic (PK) variables

Missing data and outliers of PK data are handled according to [\(3\)](#)

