6.2.4 Early discontinuation of trial medication and trial termination

The EOT activities will be performed when a patient discontinues trial medication treatment permanently.

Note: The EOT activities should not be used for temporary interruptions of trial medication.

All patients will have a follow up visit 30 days following discontinuation of trial medication, irrespective whether they complete the treatment period or prematurely discontinue trial medication.

Patients who discontinue trial medication prematurely should thereafter continue to follow scheduled visits until trial end. For patients reluctant to attend the scheduled visits after prematurely discontinuing trial medication, some trial assessments may be negotiated with exception of collection of adverse events, outcome events and concomitant therapy.

Please refer to [Section 3.3.4.1](#) for detailed procedures to be followed in case a patient wants to stop trial medication.

In case of early trial termination (e.g. based on recommendation by the DMC), a reasonable timeframe to stop the trial (perform last patient visits) will be defined and communicated to the Investigators.

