7.5 HANDLING OF MISSING DATA

There will be no imputation for safety data or for time-to-event type of endpoints. For patients who discontinue the trial treatment prematurely, all efforts will be made to follow the patients for survival and any other endpoints, including the primary and key secondary endpoints, until the end of the trial.

For the slope analysis of eGFR (CKD-EPI)_{cr}, all available on-treatment change from baseline data will be used. Patients without on-treatment data after randomisation will not be included in this analysis.

For the analysis of change from baseline to 30 days after treatment stop, only available data will be used. Only patients with post-treatment data will be used in this analysis.

For other longitudinal efficacy endpoints such as KCCQ scores, MMRM methodology will be used. Models will be run on both all observed data and all observed on-treatment data. Details of the imputation rule will be given in the statistical analysis plan.

An eGFR (CDK-EPI) reduction is considered sustained, if it is determined by two consecutive post-baseline central laboratory measurements separated by ≥ 30 days. If only one post-baseline value is available and the patient dies within 60 days of this measurement without second measurement ≥ 30 days after the first, then the eGFR reduction is also considered sustained.

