## **7.5.2 Other Secondary endpoints**

Other secondary endpoints are exploratory. No correction for multiple hypotheses testing will be made.

- *Composite renal endpoint: Time to first event of chronic dialysis or renal transplant or sustained\* reduction of  $\geq 40\%$  eGFR (CKD-EPI)cr or*
  - *(for patients with eGFR (CKD-EPI)cr  $\geq 30$  mL/min/1.73 m^2 at baseline): sustained eGFR  $< 15$  mL/min/1.73m^2*

- (for patients with  $eGFR (CKD-EPI)_{cr} < 30 \text{ mL/min/1.73 m}^2$  at baseline): sustained  $eGFR < 10 \text{ mL/min/1.73 m}^2$

\*An  $eGFR (CKD-EPI)_{cr}$  reduction is considered sustained, if it is determined by two or more consecutive post-baseline central laboratory measurements separated by at least 30 days (first to last of the consecutive  $eGFR$  values). If there is no additional measurement  $\geq 30$  days after the  $eGFR$  reduction is observed and the patient dies within 60 days of this measurement, then the  $eGFR$  reduction is also considered sustained.

Chronic dialysis is regarded as chronic if the frequency of dialysis is twice or more per week for at least 90 days.

- Time to first adjudicated HHF
- Time to adjudicated CV death
- Time to all-cause mortality
- Time to onset of DM in patients with baseline pre-DM

All time-to-event endpoints will be reported in days.

The same model and data frame as used in the primary analysis of primary endpoint will be applied to all these time-to-event endpoints. If the endpoint does not include any cause of death, a CIF plot with all-cause mortality as competing risk will be displayed; otherwise, a CIF plot with causes of death not included in the endpoint as competing risk will be displayed. For all-cause mortality a Kaplan-Meier plot will be displayed.

For time to first HHF and time to CV death, the analysis will be repeated based on investigator defined events.

- Change from baseline in clinical summary score (HF symptoms and physical limitations domains) of the Kansas City cardiomyopathy Questionnaire (KCCQ) at week 52

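### The death exception for a sustained eGFR decline ignores repeat samples taken before day 30, so a recovered fall still counts if the patient dies within 60 days of it

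*SAP*

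**What the plan says.** The renal composite is an other secondary endpoint (SAP 7.5.2). Its eGFR components are a fall of at least 40%, or a value below 15 (below 10 if baseline is under 30), and each must be sustained.

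- **Base rule, SAP 6.6.2.** The reduction must be "determined by two or more consecutive post-baseline central laboratory measurements separated by at least 30 days".
- **Death exception, SAP 6.6.2.** It begins "If there is no additional measurement", sets a limit of 30 days or more, and continues "the patient dies within 60 days of this measurement, then the eGFR reduction is also considered sustained".
- **Where it is repeated.** The same sentence stands in SAP 7.5.2 ("reduction is observed and the patient dies within 60 days of this measurement, then the") and in SAP 7.6, where it feeds three further composites: renal with CV death, with all-cause death, and with CV death or HHF.
- **Protocol 7.5.** "If only one post-baseline value is available and the patient dies within 60 days of this measurement without second measurement" at least 30 days after the first.
- **Protocol 5.1.2.** It gives the two-value, 30-day rule and no death exception.
- **Event date, SAP 6.8.2.** A sustained laboratory endpoint is dated to the first qualifying value.
- **Status, SAP 7.5.2.** "Other secondary endpoints are exploratory. No correction for multiple hypotheses testing will be made".

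SAP Section 4, which lists changes from the planned analysis, does not mention the death exception.

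**The concern.** An exception for deaths is reasonable when the patient died before a confirming sample could be taken. As worded, though, it asks only whether a sample exists from day 30 onward. It does not ask what any sample on days 1 to 29 showed. A fall that was refuted is handled like a fall that was merely unconfirmed.

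Two things are at stake. In the renal composite, which has no death component, a recovered kidney injury would be recorded as kidney progression because the patient died soon afterwards. And because the protocol and SAP state the rule in three different ways, programmers working from different sections could derive different event lists for one endpoint.

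**Working it through.** The plan gives no figure to reproduce. The check applies each wording to constructed patients.

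**Step 1: the rules.** Let the low value (a fall of 40% or more) be on day *d* and death on day *D*.

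- SAP exception: no sample on or after *d* + 30, and *D* − *d* ≤ 60.
- Protocol 7.5, read literally: the low value is the only post-baseline value, and *D* − *d* ≤ 60.
- Proposed: the SAP exception, plus every central value after *d* still meets the threshold.

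**Step 2: seven patients.** Except in row F, each also has values of −5% on days 29 and 85. The low value is −45%.

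| Patient | SAP as written | Protocol 7.5, literal | Proposed |
|---|---|---|---|
| A: low day 225, recovered (−8%) day 245, death day 280 | Event, day 225 | No event | No event |
| B: low day 225, recovered day 255, death day 280 | No event | No event | No event |
| C: low day 225, no repeat, death day 280 | Event, day 225 | No event | Event, day 225 |
| D: low day 225, still low (−44%) day 245, death day 280 | Event, day 225 | No event | Event, day 225 |
| E: low day 225, recovered day 245, death day 290 | No event | No event | No event |
| F: only post-baseline value is low, day 29; death day 80 | Event, day 29 | Event, day 29 | Event, day 29 |
| G: low day 225, recovered day 245, alive | No event | No event | No event |

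In A the repeat comes 20 days after the fall (245 − 225) and death 55 days after it (280 − 225), so both SAP conditions are met. In B the repeat is at exactly 30 days and blocks the exception. In E death is at 65 days (290 − 225), outside the window. The proposed clause changes A and nothing else.

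**Step 3: can a sample fall before day 30?** Yes. The flow chart takes eGFR at both EOT and the follow-up visit, and Protocol 6.2.4 says: "All patients will have a follow up visit 30 days following discontinuation of trial medication". The visit window is ±7 days, so days 23 to 37 are allowed after EOT. Of these 15 days, 7 (23 to 29) come before day 30. SAP 6.3 accepts follow-up values from day 23 after last intake. The renal composite uses the primary analysis's data frame (SAP 7.5.2, 7.4.1), which keeps data after treatment stop for patients who do not complete as planned. Off-drug samples after a premature stop therefore count.

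**Step 4: which endpoints change?** Every patient reached by the exception has died, so the result depends on whether that death is already a component.

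| Endpoint | Effect of a patient like A |
|---|---|
| Renal composite alone | One false event |
| Renal or all-cause death | No added event; the date moves up to 60 days earlier |
| Renal or CV death | False event only if the death is non-CV; otherwise only the date moves |
| Renal, CV death or HHF | As the row above, and only if there was no HHF |

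SAP 5.1 counts deaths of undetermined cause as CV, which narrows the last two rows further.

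**The case against.** **Protocol 5.3.4.1 already asks for a repeat.** A fall of 40% or more should lead to an extra visit 30 to preferably 60 days later, unless it was detected at EOT at trial end. Any central value then blocks the exception. This stands and keeps the numbers low. It does not close the gap, because a patient can die before that visit.

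**The intent is visible.** The rule sits under missing data, in a paragraph about an absent confirming measurement. That is fair, but the operative sentence does not say so, and a programmer following it would count patient A.

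**Protocol 7.5 may mean the same as the SAP.** If its opening condition meant one value in total, the 30-day clause after it would be redundant. The literal reading also rejects patients C and D, who have no evidence of recovery. A reader might infer that the protocol contains a deliberate recovery check; its wording does not support that. On the literal reading the two documents conflict; on the looser one they share the same gap. Either way Protocol 5.1.2 has no exception.

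**The wider harm belongs to the exception itself.** A reader might infer that a mortality difference between arms would be reported as a renal effect because of this gap. The link with mortality comes mostly from patients like C and D, whom the fix keeps as events.

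**The follow-up route is limited.** A reader might infer that the follow-up visit often precedes day 30. The documents give a window, not a distribution of actual visit days. Patients who complete treatment as planned are largely unaffected, because follow-up lies outside their time at risk (SAP 6.8.3).

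**Conclusion.** The point holds as a defect in the wording of an endpoint rule. A fall refuted by a central sample on days 1 to 29 is scored as sustained if there is no sample from day 30 onward and death comes within 60 days of the low value. Nothing elsewhere in the SAP corrects this.

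The size should be small, because several conditions must coincide: a large fall, an early central repeat showing recovery, no later sample, and an early death. A count would need the number of deaths, the share with a recent large fall, and the share of those with an early recovered sample. The documents give none of these, so no number or effect on a hazard ratio is offered. Direction is also open. Protocol 1.2.3 describes the initial eGFR drop on empagliflozin as reversible after stopping, so recovered falls could be unequal between arms, but so could deaths.

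A reader might infer that all four renal composites gain false events. They do not: the composite with all-cause death gains none, and those with CV death gain one only for a non-CV death. The renal composite is exploratory at trial level, and the primary and key secondary endpoints do not use this rule.

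**What to change.** In SAP 6.6.2, 7.5.2 and 7.6, add to the death exception that every later central eGFR value before death, if there is one, must still meet the threshold that was crossed. Align Protocol 7.5 and 5.1.2 with that wording so that one definition applies throughout, and list the change in SAP Section 4.

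The cost is one clause and one programming condition. A few renal events may be lost. In the composites where the death itself counts, the event moves from the low value to a later component event, at the latest the death and so by at most 60 days. A patient who falls, recovers and falls again before death can still be an event, dated to the later fall.

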**6.7 BASELINE, TIME WINDOWS AND CALCULATED VISITS**

For serum creatinine and values based on upon this measurement such as eGFR, baseline will be defined as the mean of all available measurements from the screening visit until start of randomised trial medication. For all other endpoints, baseline will be defined as the last available measurement before start of randomised trial medication.

Since the protocol specifies, that all measurements are taken at visit 2 before any intake of trial medication, all measurements at the first day of drug intake are assumed to qualify as baseline assessments.

For randomised patients without any treatment intake: For serum creatinine and values based on upon this measurement such as eGFR, baseline will be defined as the mean of all available measurements from the screening visit until and including the day of randomisation. For all other endpoints, baseline will be defined as the last available measurement before or on the day of randomisation.

Measurements taken after the first intake of randomised trial medication will be considered on-treatment values if they have been obtained up to end of the parameter specific follow-up period as defined in [Table 6.7: 1](#) below and will be assigned to the randomised study drug for efficacy and safety analyses.

Measurements taken after the end of the endpoint specific follow-up period after the last intake of study drug will be considered post-treatment values.

On-treatment (for OC-OT analysis) or all post-randomisation (for OC-AD analysis) efficacy and safety measurements will be assigned to visits based on time windows around the planned visit dates. These time windows are defined based on the planned number of days after the date of first administration of study drug.

The time window for the first visit after randomisation starts on the day after the first intake of study drug. The midpoint between two on-treatment visits defines the end of a time window, with the midpoint being included in the time window of the preceding visit.

Table 6.7: 1 Time windows for post-baseline efficacy measurements scheduled for each on-treatment visit for the first 3 years

Visit number	Visit label	Planned days	Time window (actual days after baseline)	
			Start	End
Endpoints assessed at each on-site visit (e.g. creatinine / eGFR)				
2	Baseline A	1	NA	1
3	Week 4	29	2	57
4	Week 12	85	58	155
6	Week 32	225	156	295
8	Week 52	365	296	449
10	Week 76	533	450	617
12	Week 100	701	618	785
14	Week 124	869	786	953
16	Week 148	1037	954	1121
18	...			
FU	FU	Trt stop + 30 days	Trt stop + 23 days	Trt stop + 45 days
KCCQ				
2	Baseline A	1	NA	1
4	Week 12	85	2	154
6	Week 32	225	155	295
8	Week 52	365	296	435
EOT	EOT / Post week 52	NA	436	Trt stop
FU	FU	Trt stop + 30 days	Trt stop + 23 days	Trt stop + 45 days

A Only values taken prior to the start of treatment with randomised study drug can be considered baseline values. Time windows will be used for assignment of measurements to scheduled visits.

For examinations that are not planned at every on-treatment visit, the time windows will be defined according to the same algorithm, based on the midpoint between the planned visit day of such an examination. Examples for eGFR and KCCQ can be found in Table 6.7: 1.

Only one observation per time window will be selected for analysis at an on-treatment visit – the non-missing value will be selected which is closest to the protocol planned visit day. If there are two observations which have the same difference in days to the planned day or if there are two observations on the same day, the first value will be used.

